Since we cannot measure improvement by EEG, and because more than one medication is often required in status epilepticus, we need a strategy with a high likelihood of controlling epileptogenic activity. Dual loading doses of ASM have been shown to provide a more definitive response in known cases of status epilepticus than using only one medication^{23,24}. The selection of phenobarbital is due to its relatively high efficacy in status epilepticus^{25,26}. The primary concerning side effect of phenobarbital is ventilatory depression. However, this effect is less relevant in this population as many of these patients already have a secure airway due to the ongoing depression in mental status and required mechanical ventilation. Therefore, this is not a significant concern for patients who are already under mechanical ventilation due to their low neurological response.

3. Specific Aims

3.1. Aim 1

Obtain a preliminary estimate of the seizure networks (SzNET) changes in moderate to severe acute brain injury (MSABI) patients after the research intervention with antiseizure medication (ASM) to support a future larger placebo controlled resting state-fMRI (rs-fMRI) clinical trial for prediction models of epileptogenicity in early SABI. The preliminary data of primary interest is the magnitude of the functional imaging SzNET response to high-efficacy pharmacological treatments in this clinical setting.

Aim 1a

Measure the improvement of the SzNET spatial total volume ([TV](#)) in MSABI patients after the intervention. The estimand of interest is the SzNET spatial TV median before and after the intervention in the target population. The intrasubject TV change ratio will be expressed as total volume reduction ([TVR](#)).

Aim 1b

Measure the improvement of the SzNET temporal power spectrum ([PS](#)) in MSABI patients after the intervention. The estimand of interest is the SzNET temporal PS median before and after the intervention in the target population. The intrasubject PS change ratio will be expressed as power spectrum improvement ([PSI](#))

3.2. Aim 2

Estimate the frequency of EEG- and EEG+ patients presenting with SzNET on their initial rs-fMRI prior to the study intervention. The estimands of interest are the proportions and differences of proportions of patients with SzNET among EEG- and EEG+ patients in this clinical setting.

3.3. Aim 3

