- The presence of SzNET will classify the patients that will receive intervention corresponding to the protocol and those that will only continue medical treatment according to care team indications in case of the presence or the absence of SzNET in the first MRI, accordingly. Outcomes will be reported as proportions and differences of proportions of patients with SzNET among EEG- and EEG+.
- Surface EEG monitoring pre-intervention (Seizures) is a binary variable collected from the total available surface EEG monitoring before rs-fMRI#1 with EEG+ and EEG- as possible values and retrieved by the investigators from the medical record or direct communication with the Epileptologist, which later must be supported in the medical records. EEG+ is defined as surface EEG with the presence of electrographic seizure, electroclinical seizure or ictal-interictal continuum.

Outcome Variables:

Each SzNET is made of one or more BOLD signal independent components that share atypical temporal or spatial features ¹¹.

- SzNET total volume (TV) is the sum of the volumes of the SzNET independent components. The TV change from before to after the intervention is a ratio expressed as the TV reduction (TVR), and is given by:

$$TVR = 1 - \frac{\sum_{i=1}^n P_i}{\sum_{i=1}^n E_i}$$

Where P is the volume of a post-treatment SzNET, E is the spatial volume of an initial SzNET and n is the amount of SzNET in each rs-fMRI.

- Power Spectrum (PS) is the sum of the power spectrum of the SzNET independent components normalized by their spatial volumes. The PS change from before to after the intervention is a ratio expressed as the PS improvement (PSI) and is given by:

$$PSI = 1 - \frac{\sum_{i=1}^n [P \int_{6.78}^{27.12} f(s)]_i}{\sum_{i=1}^n [E \int_{6.78}^{27.12} f(s)]_i}$$

Where F(S) is the power spectrum curve.

- EEG improvement Binary variable categorized in "with improvement" or "without improvement", obtained by expert's overall qualitative assessment comparing the follow-up study EEG and the clinically indicated EEG considered at the enrollment time. This qualitative assessment will be based on the EEG's background and the presence of electrophysiological signs of ictal or interictal activity.

These signs are described by the American Clinical Neurophysiology Society as:

- o Epileptiform Discharges
- o Rythmic and periodic patterns
- o Electrographic and electroclinical seizures.
- o Ictal-interictal continuum.

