It will be used to investigate the association in patients with a clear improvement of their SzNET. Such improvement will be defined as more than 0.5 TVR or 0.5 PSI threshold.

- RSN improvement is a binary variable collected by the study coordinator based on clinical records of the rs-fMRI#2, taking into consideration the spatial and temporal features and the number of canonical RSN

observed in the rs-fMRI#2. It will be used to investigate association in patients with a clear improvement of their SzNET; such improvement will be defined as more than 0.5 TVR or 0.5 PSI threshold.

- All the variables listed as exploratory will be studied for association in patients with clear improvement of their SzNET, such improvement will be defined as more than 0.5 TVR or 0.5 PSI threshold.

-

Comments regarding extended age range: 18 months to 70 years of age had heterogeneity of brain function related to both neurodevelopment and old-age related degenerative processes. However, the impact of seizure on brain networks that causes suppression of consciousness is similar through these age groups. For example when seizure occurs we expect reduction in consciousness in both young and old who have either epilepsy or acute brain injury. Patient's age may have impact on the clinical outcomes and connectivity aspects of resting state networks, for that reason we will analyze seizure networks (SzNET) different to the typical resting state networks (RSN). The analytical approach to SzNET that depend mostly on the ictal activity will be quantitative, but RSN improvement is a binary variable based on experts opinion judging the presence or absence of these normal networks that are described and used for neuroprognostication across different age groups³⁰⁻³²

Safety and Feasibility Variables:

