Investigate association between post-intervention EEG improvement and SzNET response. The outcome of interest is the relative risk of EEG improvement in patients with more than 50% improvement of their SzNET by TVR and PSI.

H_0 : there will be no difference in the EEG improvement between the patients with and without more than 50% improvement of their SzNET.

H_1 : EEG improvement will be greater in the patients with more than 50% of SzNET improvement.

There are 22 subjects used in Aim 3. We will fit logistic regression model to characterize the association between the EEG improvement with the patients with and without more than 50% improvement of either PSI or TVR. We will use the Wald test and likelihood ratio test statistics to test the null and alternative hypotheses.

Plans for Aim 4.

Investigate association between the post-intervention typical resting state networks (RSN) connectivity improvement and the SzNET response. The outcome of interest is the relative risk of improvement of the typical RSN in the patients with more than 50% of improvement of their SzNET by TVR and PSI.

H_0 : there will be no difference in the typical resting state networks connectivity improvement between the patient with and without more than 50% improvement of their SzNET.

H_1 : Median typical resting state networks connectivity improvement will be greater in the patients with more than 50% of SzNET improvement.

There are 22 subjects used in Aim 4. We will fit logistic regression model to correlate the RSN improvement with the patients with and without more than 50% improvement of either PSI or TVR and use the Wald test and likelihood ratio statistics to test the null and alternative hypotheses.

Plans for Aim 5.

Describe psychosocial functional measure outcomes and ambulatory ASM toxicity at 3 months from discharge. The outcomes of interest will be the PROMIS Emotional Distress—Anxiety— Short Form, the Neurological Disorders Depression Inventory for Epilepsy (NNDI-E), the QOLIE-10-P, the Telephonic Montreal Cognitive Assessment, and the Liverpool adverse event profile test. All will be assessed at the 3 month follow-up visit to one of the NSICU Post-Discharge clinics.

Plans for Aim 6.

Aim 6 is to assess the trial's design feasibility success in enrollment and retention by evaluating the enrollment rate and dropout rate among participants at the end of the trial.

Aim 6a

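### Section 4.3 describes the power spectrum outcome as normalized by volume, but the printed PSI formula multiplies band power by volume, so a primary outcome and one route of the responder rule lack a single definition

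*Combined protocol and SAP*

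**What the plan says.** Section 4.3 (Measurement Design, Outcome Variables) defines the temporal measure in words: "Power Spectrum (PS) is the sum of the power spectrum of the SzNET independent components normalized by their spatial volumes". It then says the pre-to-post change in PS is expressed as PSI. The printed formula is one minus a ratio of sums. Each numerator term is P times the integral of the spectrum from 6.78 to 27.12, and each denominator term is E times the same integral.

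P and E are defined once, under the TVR formula just above: "Where P is the volume of a post-treatment SzNET, E is the spatial volume of an initial SzNET". Beneath the PSI formula only the curve is explained: "Where F(S) is the power spectrum curve".

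PSI is used as follows:
- Table 2 in section 4.3 lists both PS and PSI as primary outcomes.
- Section 3.1 sets Aim 1b apart from the spatial volume of Aim 1a: "Measure the improvement of the SzNET temporal power spectrum".
- For the responder definition, section 4.3 says "Such improvement will be defined as more than 0.5 TVR or 0.5 PSI threshold". Section 8.3 builds the Aim 3 and Aim 4 predictor on "more than 50% improvement of either PSI or TVR".

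**The concern.** To normalize power by volume ordinarily means removing volume from it, by division or by averaging. The printed formula puts volume in as a factor and divides by it nowhere. The sentence and the formula therefore describe different quantities, and nothing elsewhere in the document settles which one is meant.

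Two things are at stake. First, PSI is presented as the temporal counterpart of a spatial measure. If volume is a factor in it, a shrinking network raises PSI even when the spectrum has not moved, and PSI cannot be read as evidence of temporal change separate from TVR. Second, PSI above 0.5 is one of two routes to being counted as improved in Aims 3 and 4. Section 8.3 plans 22 subjects for each of these, so one reclassified patient is 1/22 = 4.5% of the sample. The study is open-label, so a definition left open could also be settled after results are known.

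**Working it through.** The documents give no numerical PSI to reproduce, so the check evaluates the formula itself.

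**Inputs.** The PSI and TVR formulas, the definitions of P and E, and the 0.5 threshold, all from section 4.3. The percentage changes below are illustrations, not trial data.

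**Uniform changes.** Let V be component volume and f band power. Every volume falls by a fraction c and every band power by r (negative r is a rise). Then TVR = c, and PSI under each reading is:
- As printed, sum(V*f): 1 - (1-c)(1-r)
- Volume-weighted mean, sum(V*f)/sum(V): r
- P and E as time labels only, sum(f): r
- Divided by volume, sum(f/V) or sum(f)/sum(V): 1 - (1-r)/(1-c)

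| Volume | Band power | Printed | Weighted mean | Labels only | Divided |
|---|---|---|---|---|---|
| -50% | none | 0.50 | 0.00 | 0.00 | -1.00 |
| -60% | none | 0.60 | 0.00 | 0.00 | -1.50 |
| -30% | -30% | 0.51 | 0.30 | 0.30 | 0.00 |
| -60% | +20% | 0.52 | -0.20 | -0.20 | -2.00 |
| none | -60% | 0.60 | 0.60 | 0.60 | 0.60 |

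Examples for the printed column: 1 - 0.7*0.7 = 0.51, and 1 - 0.4*1.2 = 0.52. The readings agree only when volume does not change.

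**Effect on the responder rule (either route).**
- With r = 0, printed PSI equals TVR. Anyone above 0.5 on PSI is already above 0.5 on TVR, so no responder is added.
- With falls of 30% in each, TVR is 0.30 and printed PSI is 0.51. The patient is a responder although neither quantity halved.
- With r = 0.2, PSI exceeds 0.5 once (1-c)*0.8 < 0.5, that is, once c > 0.375.
- The printed form can also raise the bar. Power down 60% with volume up 30% gives 1 - 0.4*1.3 = 0.48, a non-responder.

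**Non-uniform change.** Take two components of volume 50 with band powers 3 and 1, both unchanged, and let the first shrink by 70% to 15.
- TVR = 1 - (15+50)/(50+50) = 0.35, below threshold.
- Printed PSI = 1 - (15*3 + 50*1)/(50*3 + 50*1) = 1 - 95/200 = 0.525, above threshold.
- Labels only: 1 - 4/4 = 0.
- Weighted mean: 1 - (95/65)/(200/100) = 0.27.

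Here a volume-only change that misses the TVR threshold passes on PSI as printed.

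**The case against.** The strongest reply is that the notation is loose and may mislead. The curve appears in both lower and upper case, the integral has no differential, and Table 2 uses E for the enrollment occasion. P and E might simply mark post and initial scans. Volume would then drop out and the coupling with it. This reading cannot be excluded, but it goes against the only definition the document gives, and the formula would still lack the volume normalization that the sentence promises. A division sign lost in PDF extraction is also possible, but it would have to vanish identically from numerator and denominator of a formula that is otherwise well formed.

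A reader might infer several stronger points that the documents do not support:
- *That the rule in Aims 3 and 4 becomes a volume rule with a lower bar.* A uniform volume-only fall adds nobody beyond the TVR route, and the bar can move up as well as down. What remains is that combined and non-uniform falls can reclassify patients.
- *That Aim 1b is no longer a separate primary outcome.* Section 8.3 analyses the change in PS, and Table 2 does not list PSI against Aim 1b. Aim 1b is affected only if PS is computed from the same bracketed terms. Section 4.3 makes that plausible, since it prints no other formula for PS, but does not settle it. The document also never claims that the two measures are statistically independent.
- *That text and formula must differ in sign.* This holds for simple division. A volume-weighted mean is also a normalization by volume, and it gives 0 where division gives -1.0.

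It is also fair to say that this is an uncontrolled pilot and that TV and TVR are untouched.

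**Conclusion.** The point stands as a conflict between a sentence and a formula for a listed primary outcome. With the only definitions of P and E in the document, PSI is volume-weighted power. For a halved volume with unchanged power, the candidate readings run from +0.5 through 0 to -1.0, so two analysts following section 4.3 could report opposite conclusions. The responder predictor in Aims 3 and 4 is directly affected, and Aim 1b conditionally.

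The conclusion assumes that the volume definitions under TVR carry over to PSI and that responders qualify by either route, as sections 4.3 and 8.3 say. Sections 3.3 and 3.4 join the two measures with *and*. Under that rule a uniform 51% volume loss with unchanged power would satisfy both parts of the printed definition, so the PSI definition would still matter. How many patients would change class depends on data not in the documents. This should be corrected before analysis.

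**What to change.** In section 4.3, state the one quantity intended. Use separate symbols for volume, band power and time point, define each under the PSI formula, and make the sentence and the formula agree. In section 8.3, say that Aim 1b uses the same PS that enters PSI.

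- **If PSI is meant as a temporal measure distinct from volume**, choose a form that does not move when all volumes change by the same proportion. Summed band power and the volume-weighted mean sum(V*f)/sum(V) both qualify. The weighted mean still responds to uneven shrinkage (0.27 in the two-component example), and the plan should say so if it is chosen.
- **Simple division by volume is not a neutral repair.** It would score a shrinking network with unchanged power as worsening.
- **If the product is intended**, call it volume-weighted power, and do not interpret it as evidence of temporal change separate from TVR.

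The cost is a corrected sentence and formula in section 4.3 and a matching line in section 8.3, dated before analysis. No new data are needed.

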4.2. Experimental Design

This pilot study is a stratified interventional study that will evaluate the response of an exploratory biomarker. There will be no placebo-controlled groups, and the study main intervention will be systematically assigned to all subjects with SzNET identified by the first rs-fMRI. Patients without SzNET will not receive the study treatment and will continue their medical therapy as directed by their care team. They will be included in the required analysis for aim 2 and 5. Two specialists will assess the two post-intervention follow-up studies, the rs-fMRI#2 and the repeat EEG, providing the only blinding needed. These study design elements will ensure the technical requirements necessary to calculate the sample size required for a larger trial in EEG-negative patients with SzNET-positive and explore two important aspects of the biomarker SzNET: its correlation with the EEG response of patients and the effect size of its response to the intervention ASM.

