5.7. Blinding

The Follow-up EEG will be assessed by an epileptologist blinded to rs-fMRI#2 results. Those results will not be posted in the medical records or commented with personnel outside the clinical rs-fMRI service until the follow up EEG and its comparison results should be collected. This blinding doesn't need to be removed to reassure the patient SOC.

6. Treatment Design: Procedures

Description For this uncontrolled, open-label, interventional trial, the intervention will be assigned to all enrolled patients with SzNET+ by the first rs-fMRI. The intervention and its compliance criteria are defined as receiving treatment for three to ten complete days with at least two of the following ASM regimens, simultaneously:

1. Phenobarbital 20 mg/kg intravenous loading dose
2. Levetiracetam 60mg/kg intravenous loading dose
3. Lacosamide 200 mg intravenous loading dose
4. Valproate 30 mg/kg intravenous loading dose
5. Fosphenyton 20 mg/kg intravenous loading dose

All the maintenance dose regimens will start the next day to loading dose, and dosing will be calculated for weight and age of both medications within the combination group, until the repeat rs-fMRI. As soon as possible, the research team will inform the care team that the patient has been allocated to the intervention branch so they can decide on two ASM regimens from the previous list to start the treatment. On the same day, the research team will confirm by medical charts the two ASM selected and the date and the time of the first loading dose infusions. The intervention phase takes the time between rs-fMRI#1 and follow-up rs-fMRI and EEG. The rs-fMRI#2 must be performed after at least three complete days of treatment and no later than eleven days after the beginning of the intervention phase, but in case of ASM withdrawal, the rs-fMRI#2 must be done no later than 72 hours from the last dose. As outcome measures are based on data collected the day of the second rs-fMRI, after that day, the care team will be free to adjust ASM according to what better fits the patient without compromising the protocol.

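### Section 4.3 gives RSN improvement no stated comparison with rs-fMRI#1 and no separation from the SzNET result, so the measurement itself could produce an Aim 4 association

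*Combined protocol and SAP*

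**What the plan says.** **Outcome.** Section 4.3 (Outcome Variables) states that "RSN improvement is a binary variable collected by the study coordinator based on clinical records of the rs-fMRI#2". The call rests on how many normal networks that second scan shows and on their character in space and time. Later in the same section, in the comments on the age range, it says that "RSN improvement is a binary variable based on experts opinion judging the presence or absence of these normal networks". Neither description names rs-fMRI#1 or gives a rule for what counts as improved. One makes the variable an item that the coordinator takes from records; the other makes it an expert's judgement.

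**Neighbouring outcomes.** EEG improvement is obtained by "comparing the follow-up study EEG and the clinically indicated EEG considered at the enrollment time". TVR and PSI are each written as one minus a ratio of the post-treatment to the initial value.

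**Exposure.** The SzNET response used in Aims 3 and 4 is a threshold on those ratios: "Such improvement will be defined as more than 0.5 TVR or 0.5 PSI threshold".

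**Analysis.** Section 8.3, Aim 4: "We will fit logistic regression model to correlate the RSN improvement with the patients with and without more than 50% improvement", with Wald and likelihood-ratio tests, 22 subjects and a directional alternative.

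**Blinding.** Section 4.2: "Two specialists will assess the two post-intervention follow-up studies, the rs-fMRI#2 and the repeat EEG, providing the only blinding needed". Section 5.7: "The Follow-up EEG will be assessed by an epileptologist blinded to rs-fMRI#2 results". No other masking is described.

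**The concern.** There are two gaps, and each can distort Aim 4.

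First, improvement is a change, but the definition describes the state of the networks at one scan. A patient whose normal networks were already intact at rs-fMRI#1 could be recorded as improved with no change at all. If baseline RSN status is related to SzNET response, the single-scan state will be associated with response even when RSN change is not.

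Second, the RSN call is a judgement, and the post-treatment term of TVR and PSI comes from the same scan. Section 4.2 assigns that scan to one specialist. Nothing requires the RSN call to be made without knowledge of the SzNET result, or to be fixed before that result is known. The planned blinding separates EEG from rs-fMRI, which protects Aim 3 but not Aim 4.

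Section 2.1 closes with the hypothesis that SzNET hinder recovery from coma by reducing typical RSN connectivity. Aim 4 is the test of that link, and the pilot is meant to inform a larger trial. A carry-over from the SzNET reading to the RSN call would look like the hypothesised result.

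**Working it through.** **1. The plan's own figure.** Section 9 gives a detectable correlation of 0.506 for Aim 4 (n = 22, one-sided 5%, 80% power).
- Plain Fisher z: tanh[(1.645 + 0.842)/√(22 − 3)] = tanh(0.570) = 0.516.
- With the bias term r/(2(n − 1)) and a t-based critical value: 0.5063.

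The stated figure reproduces, so the sample-size arithmetic is not at issue here. The question is what the outcome measures.

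**2. Section 4.3 set side by side.**

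| Variable | Baseline term stated? | Separation of readings stated? |
|---|---|---|
| TVR, PSI | Yes, initial value in the denominator | Not stated; calculated quantities |
| EEG improvement | Yes, EEG considered at enrollment | Yes, EEG reader blinded to rs-fMRI#2 |
| RSN improvement | No, rs-fMRI#2 only | No |

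**3. Illustration of a reading lean.** Assumed, not from the documents: no true association, a true call rate of 50%, and a shift of equal size up in SzNET responders and down in non-responders. The base case has 20 patients (section 5.1 expects 20 of the 22 treated to complete), split 10/10 by response; the split is also assumed.

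For a of n₁ responders and c of n₀ non-responders called improved, LR = 2[ℓ(a, n₁) + ℓ(c, n₀) − ℓ(a + c, n₁ + n₀)], where ℓ(x, m) = x ln(x/m) + (m − x) ln(1 − x/m). The one-sided 5% test rejects when a/n₁ > c/n₀ and LR > 2.706.

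Example: 7/10 versus 3/10 gives LR = 2[2(7 ln 0.7 + 3 ln 0.3) − 20 ln 0.5] = 2[−12.217 + 13.863] = 3.29, which rejects.

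Summing the binomial probabilities of all rejecting tables:

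| Call rate, responders/non-responders | Apparent RR | 10/10 | 11/11 | 15/7 |
|---|---|---|---|---|
| 50/50 | 1.0 | 5.8% | 6.7% | 6.5% |
| 60/40 | 0.6/0.4 = 1.5 | 25.1% | 29.0% | 26.3% |
| 70/30 | 0.7/0.3 = 2.33 | 60.9% | 67.1% | 61.7% |

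A one-sided Fisher exact test at 10/10 gives 2.1%, 12.7% and 41.8%. The levels are lower but the pattern is the same.

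**4. Illustration of state used for change.** This route needs no reader bias. Assumed: n = 22; latent baseline RSN b ~ N(0, 1); RSN change with SD 0.7, independent of everything else; SzNET response s = ρb + √(1 − ρ²)e, with e ~ N(0, 1). State is b + change > 0, true improvement is change > 0, and response is s > 0. There were 8,000 simulated trials per row, analysed with the same test.

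| ρ | Scan-2 state as outcome | True change as outcome |
|---|---|---|
| 0 | 6.2% | 6.3% |
| 0.3 | 21.8% | 6.6% |
| 0.5 | 39.7% | 6.3% |
| 0.7 | 61.6% | 6.1% |

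The documents give no value or sign for ρ. A negative ρ would act in the other direction and could hide a real association.

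**The case against.** **A before-after intent is visible.** The synopsis speaks of intervention responses of normal network connectivity. Section 2.2 says that changes in SzNET, RSNs and EEG before and after therapy will be explored. Every treated patient has an rs-fMRI#1, and the rs-fMRI#2 report may well compare the two. A reader might infer that no comparison will be made; the documents do not support that. What stands is that the operational definition does not require one, while its neighbours do.

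**The exposure is calculated.** TVR and PSI are quantitative ratios over two scans. A reader might infer that exposure and outcome are a single unmasked reading of a single scan; that is not so. What stands is narrower: the post-treatment term shares the scan with the RSN call, components must first be identified as SzNET before they are summed, and nothing says that different people make the two judgements.

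**The reader's knowledge is inferred.** The documents do not say who computes TVR and PSI, in what order, or what the rs-fMRI reader knows about SzNET response. Influence is therefore a possibility that the plan leaves open, not a documented fact.

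**Aim 1.** A reader might extend the point to Aim 1, on the ground that knowing the scan order favours improvement. TV and PS are calculated quantities, and the documents supply no mechanism or size for such an effect, so the point is confined to Aim 4.

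**Masking has limits here.** Only SzNET+ patients have rs-fMRI#2, so every first scan in a pair shows SzNET, and in a responder the second scan may be recognisable. This stands, and it limits what coded scans can achieve.

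**Weight.** RSN improvement is a secondary outcome in an uncontrolled, open-label pilot. This also stands; it bears on urgency, not on whether the definition is sound.

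**Conclusion.** The concern holds for Aim 4. Followed as written, section 4.3 supplies a single-scan state where the aim needs a change, and no section separates that expert call from the SzNET result. The statement in section 4.2 that the two-specialist arrangement is all the blinding required is not correct for Aim 4. A positive Aim 4 result could not be told apart from carry-over between readings or from baseline differences in RSN.

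The size is illustrative. With 10 per group and no true association, false rejection rises from 6% to 25% (60/40) or 61% (70/30). Using state for change gives 22% to 62% for ρ from 0.3 to 0.7, against about 6% for a true change measure. The leans, the 50% call rate, the split and ρ are all assumptions; nothing in the documents sets a plausible value. That bias could arise follows from the text; that it will arise, or how large it will be, does not.

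**What to change.** 1. In section 4.3, define RSN improvement as a paired comparison of the canonical RSN on rs-fMRI#1 and rs-fMRI#2, with a written rule for what counts as improved.
2. Have the existing rs-fMRI specialist score it, on coded scans in random order where feasible.
3. Lock the score before post-treatment TV, PS, TVR and PSI are computed and before the rs-fMRI#2 report is issued. Section 6 already holds that report until the follow-up EEG has been reported. The rs-fMRI#1 report can still be issued at once for allocation.
4. Reconcile the two descriptions in section 4.3: the expert makes the call and the coordinator records it, if that is what is meant.
5. In section 4.2, remove the claim that the existing blinding is sufficient, so far as it covers Aim 4, and describe the new step in section 5.7.
6. State that masking is partial, because SzNET may be visible on the scans and the reader may recall a case, and report this as a limitation of Aim 4. The paired rule and the score lock are useful even where masking fails.

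The cost is a wording change in sections 4.2, 4.3 and 5.7, a step in the imaging procedure, and about 22 paired reads by the existing reader. No new scans or staff are needed, and treatment is unaffected.
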